Sub-dissociative Dose Ketamine Dosing Study

NCT03714620

Date 10/17/2018

I. Study Protocol

Patient screening, enrollment, and data collection will be performed by the study investigators. All adults ≥ 18 years of age and < 60 years of age and weighing between 45-115 kg with acute abdominal, flank, back, musculoskeletal pain, or headache, with a score of 5 or more on a standard 11-point (0 to 10) VAS pain rating scale requiring intravenous analgesia, as determined by the treating attending physician, will be screened for inclusion. Exclusion criteria are as follows: pregnancy, breast-feeding, altered mental status rendering the patient unable to consent to the study, allergy to ketamine, unstable vital signs (systolic blood pressure <90 or >180 mm Hg, pulse rate <50 or >150 beats/minute, and respiration rate <10 or >30 breaths/minute), and medical history of acute head or eye injury, seizure, intracranial hypertension, chronic pain, renal or hepatic insufficiency, history of alcohol or drug abuse, and psychiatric illness. Only the first admission will be included if patients present multiple times during the study period.

i. Recruitment procedures

1. Where will recruitment occur?

Recruitment will occur in the LUMC ED upon patient's arrival and once physician has deemed it necessary that the patient receive intravenous pain medication.

2. Where and when will consent be obtained?

Consent will be obtained in the Emergency Department once it is determined that the patient meets inclusions criteria for enrollment if the patient is able to provide it.

3. Who will obtain consent?

The treating attending physician, or one of physician members of the research team, will obtain consent from the patient in the ED.

ii. Screening procedures

Patients will be screened as a convenience sample during daytime hours Monday – Friday when any of the study investigators are working and the ED clinical pharmacist is available to prepare the study drug and randomize the patients. Patients presenting to the ED with acute moderate to severe abdominal, flank, back, musculoskeletal pain, or a headache will be screened for inclusion criteria and asked to consent prior to enrollment. Consent must be obtained prior to enrollment.

b. Randomization procedures (if applicable)

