Patients will be consented for participation by one of the study investigators or the treating ED attending physician. The ED pharmacist will prepare the medication, and ensure blinding of the patient, research team, and clinical staff. The nurse caring the patient will administer the IV medication and give the patient a survey to fill out regarding pain relief and side effects at 15 minutes, 30 minutes, and 60 minutes post initiation of administration of the ketamine. Time zero will be time the drug administration is initiated. The survey will ask the patient to rate their pain using the VAS pain rating scale. Additionally, it will have a list of adverse effects, and the patient will need to rate each adverse effect using a 5 point SERSDA scale (rating each adverse event from “absent” to “very bothersome”). At the same time intervals (15, 30, and 60 minutes post initiation of drug administration), the nurse will rate the patient using the RASS scale. Vital signs will be monitored per ED protocol. Rescue analgesia will be offered at 30 minutes.

ii. Provide a schedule of all study assessments and subject activities, including a tabular representation or timeline as applicable

-Patient presents to the emergency department with acute pain

-Emergency treatment will not be delayed for the purposes of this study

-Patient seen by physician and screened for inclusion/exclusion criteria

-Patient consented for participation by research team member or physician treating the patient

-Patient randomly assigned to treatment group

-Drug prepared by ED pharmacist, administered by blinded nurse

-Time zero (0) is when nurse initiates administration of the ketamine

-Ketamine infuses over 15 minutes, ending at 15 min time mark

- Survey administered to the patient to be filled out at 15 min, 30 min and 60 min post administration of the ketamine (nurse to alert patient at specified time intervals)
- Nurse to score patient using RASS scale at 15 min, 30 min, 60 min post initiation of drug administration

II. Safety Monitoring Plan

- a. Definition of adverse events, serious adverse events

Adverse effects include dizziness, disorientation, dysphoria, nausea. Adverse events include hypoxia (<90%), hypotension (<90 systolic), vomiting, or life-threatening events.

- b. What procedures will be used to monitor subject safety?

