Ketamine is currently being used in sub-dissociative doses in the ED at LUMC to treat acute pain utilizing doses between 0.1 mg/kg- 0.3 mg/kg. The procedures to monitor safety are consistent with the ED guidelines used in current practice at LUMC. Subjects will have continuous telemetry monitoring including heart rate, respiratory rate and oxygen saturation. Vital signs (including but not limited to blood pressure measurements) will be measured and documented per standard protocol in the ED. Documented adverse side effects of sub-dissociative ketamine have included dizziness, dysphoria, and disorientation, but no serious adverse events have been noted.

- c. Who (list names) will identify, document, and report adverse events?

The blinded physician, nurse caring for patient, or one of the research team members, will identify, document, and report adverse events.

- d. What is the frequency for review of summarized safety information and who will perform the review (e.g., safety monitoring board)?

The research team will review safety information weekly.

- e. What are the stopping rules with regard to efficacy and safety?

As the target enrollment is 49 subjects per group, and we see hundreds of adult patients monthly for acute pain, we do not anticipate needing to stop the trial early. All adverse events will be reviewed and the study will be stopped immediately if we determine the AE was directly related to the subject's participation in the study.

III. Analysis Plan

Describe statistical analysis methods as appropriate. For example, will intention-to-treat methodology be used in the analysis? Will there be any sample stratification?

Descriptive statistics, including means, standard deviations, medians, interquartile ranges and percentages will be calculated for baseline variables. Comparisons of continuous parametric variables will be done using a t test. Non-parametric data will be expressed as a median and analyzed using the Mann-Whitney test. A Chi-square test or Fischer's exact test will be used to compare categorical variables as appropriate. A bivariate analysis will be performed to assess differences between SDK regimens. A P value < 0.05 will be considered significant. Microsoft Excel software and STATA version 12 will be used for data analysis.

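### Pain comparisons are planned without adjustment for the entry VAS; adjusting would cost almost nothing and bring a probably small gain in precision

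*Combined protocol and SAP*

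**What the plan says.** Eligibility (Section I) admits adults in acute pain "with a score of 5 or more on a standard 11-point (0 to 10) VAS pain rating scale", so a pain score must be obtained from every participant before enrolment. Under Study Assessments and Activities, the nurse is to "give the patient a survey to fill out regarding pain relief and side effects at 15 minutes, 30 minutes, and 60 minutes" after the infusion starts, and the survey repeats the VAS. The schedule lists no score at time zero, and nothing says that the number obtained at screening is kept as study data. The same section adds: "Rescue analgesia will be offered at 30 minutes".

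For analysis, Section III offers:

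- continuous data: "Comparisons of continuous parametric variables will be done using a t test";
- skewed or ordinal data: "Non-parametric data will be expressed as a median and analyzed using the Mann-Whitney test";
- categorical data: chi-square or Fisher's exact test;
- overall: "A bivariate analysis will be performed to assess differences between SDK regimens", not explained further.

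It also says "Descriptive statistics, including means, standard deviations, medians, interquartile ranges and percentages will be calculated for baseline variables", which may cover entry VAS but only as a summary. Section III names no outcome, time point, covariate, regression model or change score. The only sample-size statement is in the stopping-rules answer of Section II: "As the target enrollment is 49 subjects per group".

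**The concern.** Entry pain usually predicts later pain on the same scale to some degree. A test that ignores it leaves that predictable variation in the error term, so the interval for the dose difference is wider and the power lower than the same 98 patients could give. The t test and the Mann-Whitney test each have a direct adjusted counterpart: linear ANCOVA and rank-based ANCOVA. Both need only a score that eligibility already demands, provided the number is written down at the time. If it is not, adjustment cannot be done later.

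Precision is all that is at stake. Randomisation keeps the unadjusted comparison unbiased. The point concerns VAS pain only; SERSDA and RASS are not affected.

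**Working it through.** **The plan's own figure.** The 49 per group cannot be reproduced, because no power, SD or difference is given. Working backwards at two-sided 0.05 and 80% power, the detectable standardised difference is (1.960 + 0.842) × √(2/49) = 0.566. Many pairs of difference and SD return 49 (1.5/2.65, 1.7/3.0 and 2.0/3.5, for example), so none can be attributed to the plan.

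**Inputs.** From the documents: 49 per arm, 1:1 allocation, significance level 0.05, entry VAS of 5 to 10. Assumed: two-sided test, outcome SD 2.5, true difference 1.5 points, correlation r between entry and post-dose VAS of 0.2 to 0.4.

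**t test.** SE = 2.5 × √(2/49) = 0.505. With 96 df the critical value is 1.985, so the 95% CI half-width is 1.985 × 0.505 = 1.00. The noncentrality is 1.5/0.505 = 2.97, which gives power 83.6%.

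**Linear ANCOVA.** The variance is multiplied by (1 − r²) × (1 + 1/94), where the second factor is the expected cost of chance imbalance in one covariate; df = 95. Equivalent n = 49 / net variance ratio.

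| r | 1 − r² | Net variance ratio | Half-width | Power | Equivalent n per arm |
|---|---|---|---|---|---|
| 0 | 1.00 | 1.011 | 1.01 | 83.3% | 48.5 |
| 0.1 | 0.99 | 1.001 | 1.00 | 83.6% | 49.0 |
| 0.2 | 0.96 | 0.970 | 0.99 | 84.7% | 50.5 |
| 0.3 | 0.91 | 0.920 | 0.96 | 86.6% | 53.3 |
| 0.4 | 0.84 | 0.849 | 0.92 | 89.1% | 57.7 |
| 0.5 | 0.75 | 0.758 | 0.87 | 92.2% | 64.6 |

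Before rounding, the loss at r = 0 is 83.65% − 83.25% = 0.4 points.

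**Which r is plausible.** I simulated normal entry scores (mean 5 to 8, SD 2 to 2.5), rounded, capped at 10 and kept if 5 or more. An unrestricted r of 0.3 falls to 0.19–0.26, and 0.5 falls to 0.34–0.44. The entry SD is about 1.4 to 1.7. Hence r = 0.5 among enrolled patients is an optimistic bound.

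**If the t test were run on change from entry.** Section III does not exclude this. Relative to the raw score, the change-score variance is 1 + k² − 2rk, with k = entry SD/2.5. For entry SD 1.5, k = 0.6, and at r = 0.2, 0.3, 0.4 the ratio is 1.12, 1.00, 0.88. Against the better of the two t tests, ANCOVA's net variance gain is then 3%, 8% and, at r = 0.4, 1 − 0.849/0.88 = 4%. With entry SD 1.71 (scores spread evenly over 5 to 10) the gain is at most 11%.

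**Mann-Whitney branch.** Simulated power (%), 20,000 trials per setting, integer scores clipped to 0–10, 1.5-point shift. Rank-based ANCOVA here means ranked VAS regressed on ranked entry VAS, with residuals compared by group.

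| Errors | r about | t test | Linear ANCOVA | Mann-Whitney | Rank-based ANCOVA |
|---|---|---|---|---|---|
| Normal | 0.20 | 84.6 | 85.7 | 83.2 | 84.4 |
| Normal | 0.39 | 79.2 | 85.0 | 77.3 | 83.5 |
| Gamma, shape 2 | 0.21 | 88.6 | 89.4 | 92.4 | 93.2 |
| Gamma, shape 2 | 0.42 | 84.0 | 89.7 | 86.5 | 91.9 |
| Gamma, shape 1 | 0.22 | 89.9 | 90.7 | 97.0 | 97.5 |
| Gamma, shape 1 | 0.43 | 85.0 | 90.9 | 91.0 | 95.9 |

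Rank-based ANCOVA gains 0.5 to about 1 point over Mann-Whitney at r about 0.2, and 5 to 6 points at r about 0.4. With skewed errors and r about 0.2, linear ANCOVA is 3 to 6 points *below* plain Mann-Whitney, so it should not simply replace it. At r = 0, rank-based ANCOVA loses 0.1 to 0.3 points. Type I error was 4.5% to 5.4% throughout.

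**The case against.** Nothing in the plan is wrong on this point: an unadjusted comparison in a 1:1 trial is valid and defensible. The size of the gain rests wholly on an SD, a difference and a correlation that the documents do not give. Range restriction favours the low end: at r = 0.2 to 0.26 power rises only to 84.7%–85.7%, a gain of 1 to 2 points, and at r = 0.1 nothing is gained. Rescue offered at 30 minutes may weaken the correlation further at 60 minutes. VAS may not even be the main outcome, since Section III names none. And the missing time point, the handling of rescue in the analysis and the missing basis for 49 per group all matter more.

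Most of this stands, and it is why the point ranks as optional. It does not remove the point. The most that can be lost is about 0.4 power points, against 1 to 5.5 gained at r = 0.2 to 0.4. ANCOVA also spares the team a prior guess at whether raw or change scores will do better. A further fair criticism is that the choice between parametric and rank methods remains a judgement on the data. That choice is the plan's own, and the fix asks that it be made on pooled, blinded data.

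**Conclusion.** The point holds as an optional improvement. No method named in Section III is stated to use the entry VAS, although eligibility requires that score and the scale is repeated after dosing. Under the assumptions above (SD 2.5, difference 1.5, two-sided 0.05, r = 0.2 to 0.4, 49 per arm), adjustment is worth 1 to 5.5 power points, or about 1.5 to 9 extra patients per arm (50.5 − 49 to 57.7 − 49). The probable value lies towards the lower end, because the cut-off at 5 narrows the entry scores. Confidence is medium: the facts about the plan are clear, but the correlation that drives the size is unknown.

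**What to change.** In the assessment schedule, record the numeric entry VAS as a study variable, ideally just before time zero. In Section III, add wording such as:

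> One pain time point (15, 30 or 60 minutes) is named before the dose code is opened. VAS at that time is compared by linear regression on dose group and entry VAS, reporting the adjusted mean difference (0.15 minus 0.3 mg/kg) with 95% CI. If the pooled, blinded data are judged non-parametric, medians are reported and the test is rank-based ANCOVA on entry VAS, replacing the unadjusted Mann-Whitney test.

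If 60 minutes is chosen, also state how patients given rescue after the 30-minute offer are handled in the analysis. Adjustment does not settle the time point or the rescue question; the plan must answer both in any case. The SERSDA and RASS analyses are unchanged.

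The cost is a few sentences, one recorded value per patient, one degree of freedom and a few commands in the STATA version already named.
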